Information concerning any adverse events will be obtained by the Clinical Examiner from the subjects at the time of sensitivity assessment. All observed or voluntarily reported adverse events regardless of test group or suspected causal relationship with a test product shall require immediate notification within 24 hours to the IRB and the Sponsor or its designated representative, during a reporting period beginning from the time that the subject first provides informed consent, which is obtained prior to the start of the clinical study, i.e. prior to the subject undergoing any study-related procedure and/or receiving any test product, through to and including 30 calendar days after the last administration of the test product. Any adverse event occurring any time after the reporting period must be promptly reported to assess whether it meets the criteria for classification as a serious adverse event requiring immediate notification to the Sponsor or its designated representative. The Principal Investigator is required to assess causality, and for all adverse events, sufficient information should be obtained by the Principal Investigator to try to determine the causality of the adverse event. For adverse events with a suspected causal relationship to a test product, follow-up by the Principal Investigator is required until the event or its sequelae are resolved or stabilized at a level acceptable to the Principal Investigator, and the Sponsor concurs with that assessment.

STATISTICAL PROCEDURES:

Product Efficacy Data Analysis:

Efficacy outcomes: The primary efficacy outcome will be the decrease in cold air stimulus sensitivity (VAS score) from baseline to 8 weeks. The secondary efficacy outcome will be the increase in tactile stimulus force from baseline to 8 weeks. Additional outcomes will include changes in cold air stimulus sensitivity and tactile stimulus force from baseline to 4 weeks.

(1) Data Analysis for Efficacy of the Primary Evaluation Item

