Comparisons among the three groups for differences in the primary and secondary efficacy outcomes at each time point will be analyzed using analysis of covariance; because of the stratified randomization, age, gender, and baseline VAS cold air sensitivity will be included as covariates. Pre-planned post-hoc comparisons include: 1) pair-wise comparisons of the test product and the positive control against the placebo, to demonstrate effectiveness and 2) 95% confidence intervals (CI) for the ratio of means for the nano-HAP test product to the positive control to demonstrate non-inferiority of the test product with the positive control. Non-inferiority will be demonstrated if the lower

bound of the 95% CI falls within the 20% non-inferiority margin. If the data are log-normally distributed, then the analyses will be done on the log-transformed data. If the 95% CI for the difference between the test paste and the positive control is transformed back to the original scale, the back-transformed CI is a 95% CI for the ratio of means. If data are normally distributed, the 95% CI will be computed using Fieller's theorem, and the other condition that must be met to show non-inferiority is that the reference (i.e. positive control) mean must be significantly different from zero using a one-sided test. A 5% significance level will be used for all tests. From the results obtained for the placebo and positive control groups, it will be confirmed whether the non-inferiority margin used in the trial (20%) was appropriate or not.

(2) Data Analysis for the Efficacy of the Secondary Evaluation Item

Repeated measures analysis of covariance will be used for comparison between the 4-week and 8-week outcomes within each group. Interactions of the treatment effect with age, gender, and tactile sensitivity will be examined to evaluate significance of differential effects of the treatment by patient characteristics.

Sample Size Calculation

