Based on data from prior studies,^{A2, A5, A6} the coefficients of variation (the ratio of the standard deviation to the mean (SD/Mean)) at 8 weeks in cold air stimulus sensitivity and tactile stimulus force are estimated to be 0.500 and 0.400, respectively.^{A7} Based on this COV, the power and sample size for non-inferiority t-tests from a parallel-groups design is calculated with the statistical hypotheses expressed in terms of mean ratios (Treatment Mean / Reference Mean) instead of mean differences. Using the software PASS 2019, v19.0.1, the sample size for Non-Inferiority Tests for the Ratio of Two Means is calculated from R Package of Chow^{A8} by inputting the following information;

Option	Value
Design Tab	
Solve For:	Sample Size
Higher Means Are:	Better (H1: $R > 1 - NIM$)
Power:	0.80
Alpha:	.050
Group Allocation:	Equal ($N1 = N2$)
NIM (Non-Inferiority Margin):	0.2
R1 (Actual Ratio):	1.0
COV (Coefficient of Variation):	0.5 0.4

The following results were generated by the software.

Non-Inferiority Tests for the Ratio of Two Means

Numeric Results for a T-Test

R = Treatment Mean / Reference Mean

Higher Means are Better

Hypotheses: H0: R ≤ 1 - NIM vs. H1: R > 1 - NIM

Target Power	Actual Power	N1	N2	N	-NIM	Bound R0	R1	COV	Alpha
0.80	0.80419	38	38	76	-0.200	0.800	1.000	0.400	0.050
0.80	0.80557	57	57	114	-0.200	0.800	1.000	0.500	0.050

The highlighted numbers are the sample sizes if primary outcome measure is based on cold air (green) or tactile stimuli (yellow). The sample sizes were calculated for nano-HAP (N1) and KNO₃ (N2) groups. (By default the placebo group will have the same sample size).

Report Definitions

Target power is the desired power value (or values) entered in the procedure. Power is the probability of rejecting a false null hypothesis.

Actual power is the power obtained in this scenario. Because N1 and N2 are discrete, this value is often (slightly) larger than the target power.

N1 and N2 are the number of items sampled from each population.

N is the total sample size, N1 + N2.

-NIM is the magnitude and direction of the margin of non-inferiority. Since higher means are better, this value is negative and is the distance below one that is still considered non-inferior.

R0 is the corresponding bound to the non-inferiority margin and equals 1 - NIM.

R1 is the mean ratio (treatment/reference) at which the power is computed.

COV is the coefficient of variation on the original scale.

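### The 20% non-inferiority criterion is stated for two different quantities, and the 80% power comes from a log-normal model that the primary outcome is unlikely to meet

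*Combined protocol and SAP*

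**What the plan says.** All references are to the combined protocol and SAP.

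- **Opening objective paragraph.** Non-inferiority is declared on the mean percentage reduction of sensitivity, nano-HAP against KNO3, with a margin of 20%.
- **Efficacy outcomes, under Product Efficacy Data Analysis.** "The primary efficacy outcome will be the decrease in cold air stimulus sensitivity (VAS score) from baseline to 8 weeks". This is an absolute decrease in millimetres, not a percentage.
- **Data Analysis for Efficacy of the Primary Evaluation Item.** The decision uses the lower bound of a 95% CI for the ratio of means, nano-HAP to KNO3. The method depends on the data: "If the data are log-normally distributed, then the analyses will be done on the log-transformed data"; "If data are normally distributed, the 95% CI will be computed using Fieller's theorem", with the added condition that the positive-control "mean must be significantly different from zero using a one-sided test". ANCOVA is planned: "because of the stratified randomization, age, gender, and baseline VAS cold air sensitivity will be included as covariates". All tests use a 5% significance level.
- **Sample Size Calculation.** The non-inferiority test is for a ratio of two means: bound R0 = 0.800, true ratio 1.0, alpha 0.05, one-sided. Power is 0.80557 at 57 per group (COV 0.5) and 0.80419 at 38 per group (COV 0.4). The coefficients of variation "at 8 weeks in cold air stimulus sensitivity and tactile stimulus force are estimated to be 0.500 and 0.400". The report definitions add: "Since higher means are better, this value is negative and is the distance below one that is still considered non-inferior". The closing power statement gives the limit of the mean ratio as 20%, where the table has 0.800.

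**The concern.** There are two problems, the first more important.

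1. **The criterion.** Mean percentage reduction weights each subject by the inverse of his or her baseline; the ratio of mean decreases does not. The objective's wording can also be read as 20 percentage points instead of a relative 20%. The pass or fail decision for the primary claim could depend on which sentence is followed.

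2. **The power.** The figure that justifies 57 completers per group should belong to the analysis that will be run. A log-normal variable is strictly positive. Baseline VAS is at least 30 mm on a 0 to 100 mm scale, so the decrease can lie anywhere from -70 to +100 mm, and a single non-positive value leaves its logarithm undefined. The branch more likely to apply is Fieller, for which no power is stated. The plan also gives no rule for choosing between the branches and none for data that fit neither.

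The variable behind the COV adds to the second problem. The text attaches it to sensitivity at 8 weeks, literally a score for which lower is better, yet the calculation treats higher as better, which fits a decrease.

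**Working it through.** **1. Do the two criteria agree?** An invented example, point estimates only. In each arm half the subjects start at 40 mm and half at 80 mm.

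| Arm | Decrease from 40 mm | Decrease from 80 mm | Mean decrease | Mean percentage reduction |
|---|---|---|---|---|
| KNO3 | 30 (75%) | 40 (50%) | 35 mm | 62.5% |
| nano-HAP | 18 (45%) | 40 (50%) | 29 mm | 47.5% |

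- Ratio of mean decreases: 29/35 = 0.83, above 0.80.
- Ratio of mean percentage reductions: 47.5/62.5 = 0.76, below 0.80.
- Difference in percentage reduction: 62.5 - 47.5 = 15 points, inside 20 points.

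The relative and points readings also differ in general. If KNO3 reduced sensitivity by 50% (illustrative), a 20-point margin sets the limit at 30%; a ratio of 0.80 sets it at 40%.

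**2. Reproducing the stated power.** Inputs from Sample Size Calculation: n = 57, COV 0.5, R0 = 0.80, R1 = 1, one-sided 0.05. Log-normal ratio model:

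- log-scale SD = sqrt(ln(1 + 0.5²)) = 0.4724
- noncentrality = ln(1/0.8) / (0.4724 × sqrt(2/57)) = 0.2231 / (0.4724 × 0.1873) = 2.522, df = 112
- power = 0.80557, as stated.

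The same formula at n = 38 and COV 0.4 gives 0.80419, also as stated. Two alternatives at n = 57 and COV 0.5 do not reproduce the figure: the normal-data ratio test gives 0.758, and a plain difference with SD 0.5 and margin 0.2 gives 0.688.

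**3. How likely is a non-positive decrease?** If decreases are normal with COV 0.5 (assumed), P(decrease ≤ 0) = Φ(-1/0.5) = 2.3%. Among 2 × 57 = 114 subjects, the chance of at least one is 1 - 0.97725^114 = 93%.

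**4. Power of the Fieller branch.** For normal data the test at the bound is on the contrast nano-HAP mean - 0.8 × KNO3 mean, whose variance is SD²(1 + 0.64)/n. With COV 0.5 assumed to describe the decrease, and no adjustment:

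- noncentrality = 0.2 / (0.5 × sqrt(1.64/57)) = 0.2 / (0.5 × 0.1696) = 2.358, df = 112
- power = 75.8% at one-sided 0.05; 64.7% at one-sided 0.025 (lower limit of a two-sided 95% CI).

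A simulation of the Fieller limit itself (100,000 runs) gave 75.9% and 64.8%. With all 64 per group analysed, the formula gives 79.97% and 69.8%.

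**5. Effect of the planned ANCOVA.** If the covariates explain a share R² of the variance of the decrease, the noncentrality is divided by sqrt(1 - R²). At 57 per group and COV 0.5:

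| R² (assumed) | One-sided 0.05 | One-sided 0.025 |
|---|---|---|
| 0 | 75.8% | 64.7% |
| 0.10 | 79.5% | 69.3% |
| 0.20 | 83.5% | 74.3% |
| 0.30 | 87.6% | 79.8% |
| 0.50 | 95.2% | 91.1% |

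Power of 80% needs R² of about 0.11 at one-sided 0.05 and about 0.30 at one-sided 0.025.

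**6. Sensitivity to the COV.** Unadjusted Fieller power, 57 per group, one-sided 0.05, for a COV of the decrease of 0.40 / 0.45 / 0.50 / 0.55 / 0.60 (assumed range): 90 / 83 / 76 / 69 / 62%.

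**The case against.** The strongest reply is that the plan already handles the analysis side. The log branch is conditional, Fieller is supplied for normal data, and the condition on the KNO3 mean is stated. This stands: a reader might infer that the plan would take logarithms of zero or negative decreases, and it does not require that. Nor do the documents say that non-positive values will occur; the 93% above rests on an assumed distribution. A planning model may also be an approximation, and the note "COV is the coefficient of variation on the original scale" is compatible with a calculation on a transformed scale.

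A reader might also infer that the trial is underpowered, with a true power of 76%. The documents do not support that. The 75.8% ignores the planned ANCOVA, assumes that 0.5 is the COV of the decrease, and uses one-sided 0.05, whereas the decision rule refers to a 95% CI whose sidedness is not stated. At the planning alpha the unadjusted gap is about 5 points (80.6 - 75.8), and a modest R² closes it.

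The COV wording may be shorthand for the change. The sources behind the 0.5 are not available here, so only the ambiguity can be claimed.

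None of this removes the conflict between percentage reduction and ratio of mean decreases, or the absence of a power figure for the Fieller branch.

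**Conclusion.** The concern holds as an inconsistency in the criterion and a gap in the power justification. It is not an arithmetic error: 0.80557 is correct for its own model.

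- **Criterion.** The documents define the primary non-inferiority comparison as two different quantities, and the same data can pass on one and fail on the other. This rests on the text alone.
- **Power.** The 80% belongs to a branch that is unlikely to be usable for a decrease in VAS. For the Fieller branch at 57 per group, unadjusted power is about 75.8% (one-sided 0.05) or 64.7% (one-sided 0.025), if COV 0.5 describes the decrease and the true ratio is 1. After ANCOVA it reaches 80% if the covariates explain about 11% or about 30% of the variance respectively. The documents give neither an R² nor a correlation between baseline and week 8, so power may be below or above 80%. A shortfall is possible but not proven.

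**What to change.** 1. **One criterion.** The sponsor chooses between percentage reduction and ratio of mean decreases and uses that choice in the opening objective, the efficacy outcomes, the primary analysis and the sample-size text. If it is the ratio of mean decreases, state the bound as 0.80 everywhere, including where the limit of the mean ratio now reads 20%. If it is percentage reduction, say whether 20% is relative or in percentage points.
2. **One analysis.** If the ratio of mean decreases is chosen, drop the data-dependent log branch for this outcome. Prespecify the Fieller CI on ANCOVA-adjusted means, evaluated at the overall covariate means because the ratio depends on where they are taken, and keep the condition on the KNO3 mean.
3. **Matching power.** State which variable the COV describes. Restate power for the Fieller analysis at the confidence level that will decide non-inferiority, unadjusted and over a range of COVs and assumed R².

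The cost is wording in these sections and one recalculation. No new data and no extra enrolment are asked for. The downside is that the stated unadjusted power may fall below 80%.

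### The only repeated-measures analysis compares week 4 with week 8 within each arm, so nothing planned tests whether the difference between pastes changes between those visits

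*Combined protocol and SAP*

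**What the plan says.** All of this comes from the Statistical Procedures part of the combined protocol and SAP.

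- **Outcomes** (Product Efficacy Data Analysis). Primary: "The primary efficacy outcome will be the decrease in cold air stimulus sensitivity (VAS score) from baseline to 8 weeks". Secondary: "The secondary efficacy outcome will be the increase in tactile stimulus force from baseline to 8 weeks". Week 4 enters as follows: "Additional outcomes will include changes in cold air stimulus sensitivity and tactile stimulus force from baseline to 4 weeks".
- **Between-arm analysis** (item 1, primary evaluation item). The method is stated like this: "Comparisons among the three groups for differences in the primary and secondary efficacy outcomes at each time point will be analyzed using analysis of covariance", adjusted for age, gender and baseline cold-air VAS. The planned contrasts are "pair-wise comparisons of the test product and the positive control against the placebo, to demonstrate effectiveness" and, for non-inferiority, "95% confidence intervals (CI) for the ratio of means for the nano-HAP test product to the positive control". A 5% level is set for every test.
- **Repeated-measures analysis** (item 2, secondary evaluation item). The method is stated like this: "Repeated measures analysis of covariance will be used for comparison between the 4-week and 8-week outcomes within each group". The next sentence lists the interactions: "Interactions of the treatment effect with age, gender, and tactile sensitivity will be examined". Visit is not among them, and the terms of the repeated-measures model are not given.

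**The concern.** The change from week 4 to week 8 inside one arm is an uncontrolled before-and-after comparison. By the Summary of Study Design, the three pastes share a base formulation and a brushing routine. The outcomes are subject-reported: a mark on a VAS line, or saying when pressure is uncomfortable. The section on applying the stimulus itself recognises that anticipation can alter perception. Any movement within an arm therefore combines the active ingredient with base paste, brushing, placebo response, repeat testing and time. Randomisation protects only differences between arms.

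The comparison is placed under an efficacy heading and carries a significance test, yet it estimates none of the declared outcomes, all of which are changes from baseline. The related question that randomisation could answer, whether the gap between pastes widens or narrows from week 4 to week 8, has no planned estimate with a confidence interval and no planned test. At stake is what can properly be said about speed or persistence of effect relative to KNO3 or placebo.

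**Working it through.** **1. The plan's own figures.** The plan gives no sample size or power for the week 4 versus week 8 comparison, so the only figures to reproduce are those for non-inferiority (Sample Size Calculation). On the log scale, σ = √ln(1 + COV²), the non-centrality is −ln(0.8) / (σ√(2/n)), df = 2n − 2, one-sided alpha 0.05.

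- Cold air, COV 0.5: σ = √ln 1.25 = 0.472; n = 57; non-centrality 0.2231 / (0.472 × 0.1873) = 2.52; power 0.80557, as stated.
- Tactile, COV 0.4: n = 38; power 0.80419, as stated.
- Dropout: 57 / 0.90 = 63.3, rounded up to 64 per arm, as stated.

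The figure carried forward is 57 completers per arm.

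**2. Which contrasts are planned.**

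| Question | Planned analysis | Uses randomisation? |
|---|---|---|
| Do pastes differ at week 4? | ANCOVA, item (1) | Yes |
| Do pastes differ at week 8? | ANCOVA, item (1) | Yes |
| Did an arm move from week 4 to week 8? | Repeated-measures ANCOVA, item (2) | No |
| Does the difference between pastes change from week 4 to week 8? | None stated | – |

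The first row reads the time-point wording of item (1) as including week 4. With week 4 changes listed as additional outcomes, that wording would otherwise have no purpose.

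**3. How often within-arm tests would disagree when the arms do not differ.** Let every arm have the same true 4-to-8-week change, and let each within-arm test have power p. The arms are independent, so:

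- three arms not all agreeing: 1 − p³ − (1 − p)³;
- two arms disagreeing: 2p(1 − p).

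At p = 0.5 these are 0.75 and 0.50, the maxima. At p = 0.2 or p = 0.8 they are 0.48 (three arms) and 0.32 (two arms).

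To tie p to this trial's size, take a two-sided 5% paired t-test in 57 subjects (df = 56, non-centrality d√57). Here d is the true change in units of the SD of individual change. It is an assumption; the documents give no expected change, SD of change or correlation between visits.

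| Assumed d | Power in one arm | Three arms give mixed verdicts | Two arms disagree |
|---|---|---|---|
| 0 | 0.050 | 14% | 9.5% |
| 0.1 | 0.115 | 31% | 20% |
| 0.2 | 0.317 | 65% | 43% |
| 0.26 | 0.488 | 75% | 50% |
| 0.3 | 0.605 | 72% | 48% |
| 0.4 | 0.843 | 40% | 26% |
| 0.5 | 0.960 | 11.5% | 7.7% |

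The rate rises and then falls, so the low end of the range lies at d = 0.5.

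**4. The randomised alternative.** In 20,000 simulated trials at d = 0.26, the three within-arm tests disagreed in 75.6%, matching the formula. A group-by-time F test on the same data rejected in 5.1%, close to its nominal level.

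**The case against.** The strongest case against is that the plan already compares the pastes where it matters. Item (1) gives adjusted, randomised comparisons at both visits, including contrasts with placebo and the ratio to KNO3. Both study objectives, non-inferiority to KNO3 and superiority to placebo, rest on those and not on item (2). In the same completers, with the same covariates and on the untransformed scale, subtracting the week 4 contrast from the week 8 contrast already gives the between-arm difference in change. Only its standard error and test are missing. Asking whether an arm moved between visits is also a legitimate descriptive question.

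All of that stands, and it limits the point. Four stronger readings are tempting, and the documents do not support them:

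- *The plan has no randomised comparison over time.* It has one at each visit. What is missing is the comparison of the two.
- *Three separate tests are planned, one per arm.* The wording also fits one model over all arms with within-group visit contrasts. The gap remains either way, because the contrast named is within-group and the model terms are not stated.
- *The sponsor will rank pastes by which within-arm test is significant.* Nothing says so. It is a foreseeable misreading of results, not a stated intention.
- *Mixed verdicts should be expected 75% of the time.* That is the peak of the formula, at an assumed 50% power, and it measures a misuse that the plan does not propose.

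**Conclusion.** The point holds as a gap in a secondary analysis. The one repeated-measures analysis uses a contrast without a concurrent control, places it under an efficacy heading with a significance level, and specifies no treatment-by-visit term. It can describe how an arm moved between visits. It cannot attribute that movement to the paste, nor show that pastes differ in it.

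The illustration of size is mixed verdicts in about 11.5% to 75% of trials when all arms change equally. It rests on 57 completers per arm, two-sided 5% tests, independent arms and assumed changes of 0 to 0.5 SD. It shows only that significance in one arm and not in another is no evidence of a difference between pastes; it does not predict this trial's results. The primary non-inferiority test, the placebo comparisons and the sample size are untouched.

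**What to change.** In item (2), replace the within-group comparison with a single repeated-measures ANCOVA over both post-baseline visits and all three arms. Its terms are treatment, visit, treatment-by-visit and the covariates of item (1): age, gender and baseline cold-air VAS. State which outcome or outcomes it applies to. Report the between-arm differences in the 4-to-8-week change with 95% CIs. Present within-arm changes as descriptive estimates and say that they are not evidence of efficacy.

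The cost is a few lines of SAP wording, best settled before the treatment code is broken. The data, visits and number of subjects stay the same.

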Alpha is the probability of rejecting a true null hypothesis.

Summary Statements

Group sample sizes of 38 in the first group and 38 in the second group achieve 80% power to detect non-inferiority using a one-sided, two-sample t-test. The margin of non-inferiority is 20%. The true ratio of the means at which the power is evaluated is 1.000. The significance level (alpha) of the test is 0.050. The COV of both groups are assumed to be 0.400.

With a sample size of at least 57 subjects per group completing the study, a non-inferiority test of means using two one-sided tests achieves 80% power at a 5% significance level for cold air stimulus sensitivity when the true ratio of the means is 1.000 and the non-inferiority limit of the mean ratio is 20%. Because the COV for tactile stimulus force is smaller, the study will have higher power for that outcome. To allow for 10% dropout, the study will enroll 64 subjects per group (192 subjects in total). Sample size calculations were performed using PASS 2019 (Kaysville, UT).

Dropout-Inflated Sample Size

Dropout Rate	Sample Size			Dropout-Inflated Enrollment sample size			Expected Number of Dropouts		
	N1	N2	N	N1'	N2'	N'	D1	D2	D
10%	38	38	76	43	43	86	5	5	10
10%	57	57	114	64	64	128	7	7	14

Definitions

Dropout Rate (DR) is the percentage of subjects who are expected to be lost at random during the course of the study and for whom no response data will be collected (i.e. who will be treated as "missing").

[figure not shown]
N1, N2, and N are the evaluable sample sizes at which power is computed. If N1 and N2 subjects are evaluated out of the N1' and N2' subjects that are enrolled in the study, the design will achieve the stated power.

N1', N2', and N' are the number of subjects that should be enrolled in the study in order to end up with N1, N2, and N evaluable subjects, based on the assumed dropout rate.

After solving for N1 and N2, N1' and N2' are calculated by inflating N1 and N2 using the formulas $N1' = N1 / (1 - DR)$ and $N2' = N2 / (1 - DR)$, with N1' and N2' always rounded up. (See references A7, pages 52-53, or A8, pages 32-33.)

D1, D2, and D are the expected number of dropouts. $D1 = N1' - N1$, $D2 = N2' - N2$, and $D = D1 + D2$.

Chart Section

Criteria for Test Aborting and Drop-out

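### The 80% power is computed at one-sided 5%, but non-inferiority is judged by a 95% confidence interval; under that rule 57 per group gives about 70.5% power

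*Combined protocol and SAP*

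**What the plan says.** **Decision rule.** Under Data Analysis for Efficacy of the Primary Evaluation Item, the plan calls for "95% confidence intervals (CI) for the ratio of means for the nano-HAP test product to the positive control". Non-inferiority is shown if the lower "bound of the 95% CI falls within the 20% non-inferiority margin". The interval is either back-transformed from a log-scale difference or computed by Fieller's theorem. It is never described as one-sided, and no 90% interval appears anywhere. The same section adds "A 5% significance level will be used for all tests" without giving sidedness.

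**Sizing.** Under Sample Size Calculation, the software input is alpha .050 and the output lists one hypothesis pair: "Hypotheses: H0: R ≤ 1 - NIM vs. H1: R > 1 - NIM". The Summary Statements confirm, for the 38-per-group row, "80% power to detect non-inferiority using a one-sided, two-sample t-test" and "The significance level (alpha) of the test is 0.050". For the 57-per-group case, which sets the trial's size, they say that "a non-inferiority test of means using two one-sided tests achieves 80% power at a 5% significance level".

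**The concern.** The trial is powered for one test and decided by another. The lower limit of a two-sided 95% interval is a one-sided 2.5% test; a one-sided 5% test matches the lower limit of a 90% interval. The stated 80% belongs to the second and the decision rule to the first.

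The phrase two one-sided tests adds a third possibility. It names an equivalence procedure with both a lower and an upper limit, whereas the software output has only the lower one.

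The stake is the primary claim. The 95% rule is the stricter of the two, so the type I error is not inflated; the harm is that power is overstated. With two significance levels in the text, there is also room for argument after unblinding if the lower limit falls near 0.80.

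**Working it through.** **Inputs, all from Sample Size Calculation and its Summary Statements:** coefficient of variation (COV) 0.5 for cold air and 0.4 for tactile; ratio bound 0.80; true ratio 1.0; 57 evaluable per group; 10% dropout; 64 enrolled per group.

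**Method:** two-sample t-test on the log scale.

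- Log-scale SD: σ = √ln(1 + COV²) = √ln(1.25) = 0.4724
- Distance from the true ratio to the bound: −ln(0.8) = 0.2231
- Standard error at 57 per group: 0.4724 × √(2/57) = 0.0885
- Noncentrality: 0.2231 / 0.0885 = 2.522, with 2 × 57 − 2 = 112 degrees of freedom
- Power = P(noncentral t > critical t)

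**Step 1: reproduce the plan's figures (one-sided 0.05).**

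| COV | n per group | Plan | Recomputed |
|---|---|---|---|
| 0.5 | 57 | 0.80557 | 0.80557 |
| 0.4 | 38 | 0.80419 | 0.80419 |

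The smallest sample sizes reaching 80% are 57 and 38, and 57/0.9 = 63.3 rounds up to 64. Everything matches, so this is the plan's own method.

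**Step 2: change only the critical value.** At 112 degrees of freedom it rises from 1.659 (one-sided 0.05) to 1.981 (one-sided 0.025).

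| Case, cold air, one-sided 0.025 | Power |
|---|---|
| 57 per group | 0.705 |
| 64 per group (no dropout) | 0.755 |
| 71 per group | 0.798 |
| 72 per group | 0.804 |

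So 80% needs 72 evaluable per group. At 10% dropout that is 72/0.9 = 80 enrolled per group and 3 × 80 = 240 in total, against the planned 64 and 192.

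**Step 3: side checks.**

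- Tactile outcome (COV 0.4), 57 per group, one-sided 0.025: 0.866. It is not affected.
- Original-scale test of the Fieller type, cold air, 57 per group: 0.758 at one-sided 0.05 and 0.647 at 0.025. The plan uses this route if the data are normal, and the shortfall is then larger.
- Two one-sided tests taken literally at 5%, with an upper limit of 1.25 (an assumption; the plan gives none): about 0.61.

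**The case against.** **The interval may have been meant as one-sided.** Only the lower bound is used, the general level is 5% without sidedness, and the text never says two-sided. If a one-sided 95% bound was meant, 80% stands. This is the less natural reading: back-transformed and Fieller intervals are ordinarily two-sided, and the plan marks only the test of the reference mean as one-sided. Even on this reading the text must be corrected to say so.

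**Covariate adjustment may recover power.** The primary analysis is analysis of covariance with age, gender and baseline VAS. As an illustration, covariates explaining about 20% of the log-scale variance would bring power at 57 per group to about 80% at one-sided 0.025, and about 10% would do so at 64. This is fair, and it means 70.5% is the power under the plan's sizing method rather than a forecast of the trial's true power. But the documents give no covariate correlation, and the stated 80% does not rely on one.

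**Re-running the calculation at 0.025 would change the sample size.** The run solves for sample size, so with the new alpha it would return 72. That is correct; keeping 57 means solving for power at a fixed n, and saying openly that power is below 80%.

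**Two one-sided tests is probably a slip.** Probably so, since the output has a single hypothesis. The 0.61 figure is therefore a side calculation, and the conclusion does not depend on it.

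**Conclusion.** The concern holds. The arithmetic in the plan is right for the test it describes, but that test is not the one that decides the trial. Under the written 95% interval rule, power for the primary cold air comparison is about 70.5% with 57 evaluable per group and about 75.5% with all 64. A truly equal product would be missed about 30% of the time rather than 20%.

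These figures assume an ordinary two-sided 95% interval, the plan's unadjusted log-scale t-test, a COV of 0.5 and a true ratio of 1.0.

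**What to change.** 1. Keep the 95% interval rule in the analysis section, and state that it is two-sided, so that the non-inferiority test is one-sided at 2.5%.
2. In Sample Size Calculation and the Summary Statements, set alpha to 0.025 one-sided. Solve for power at the planned size, and report about 70% at 57 evaluable per group and about 75% if all 64 are evaluable, for the unadjusted log-scale test.
3. Replace the reference to two one-sided tests with one one-sided test at 2.5%.

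This costs only wording and a less favourable stated power; enrolment stays at 192. If the sponsor wants to keep 80% under this rule, the price is 72 evaluable and 80 enrolled per group (240 in total). If a one-sided 5% rule was intended, the plan must instead specify a 90% interval and justify it before unblinding.
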